13.7 Reporting and Exclusions

All eligible participants included in the study will be evaluable for analysis.

13.7.1 Evaluation of Toxicity

All patients will be evaluable for toxicity from the time of their first treatment.

13.7.2 Evaluation of the Primary Efficacy Endpoint

All eligible participants included in the study will be assessed for response/outcome to therapy for the primary endpoint, even if there are major protocol therapy deviations.

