13.2 Sample Size, Accrual Rate and Study Duration

The total planned sample size is 152 patients (76 patients on each arm), which is calculated based on the number of randomized patients and defines the intention-to-treat population for efficacy analysis. The study is sized to have 82.3% power to detect improvement of median PFS from 4 months with neratinib monotherapy to 6 months with neratinib + fulvestrant (HR=0.67) using a stratified logrank test with a one-sided alpha level of 0.1, and final analysis to occur when 125 PFS events are observed. This assumes that the total planned sample size is enrolled at a constant accrual over 18 months with 6 months of additional follow-up, and a constant hazard of PFS and dropout such that 5% of patients are lost-to-follow-up at 1 year. One futility analysis is planned at 50% information (63 PFS events) and will stop early if the Z-statistic from the logrank test is less than 0 (i.e. observed HR from a Cox model > 1.0). No early stopping for efficacy will be considered. Power and sample size were calculated using East v6.4 (Cytel Inc., Cambridge MA).

We anticipate enrollment of approximately 8.5 patients per month. Patients will be followed for up to five years after removal from study or until death, whichever occurs first.

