13.4 Analysis of Primary Endpoints

The primary analysis of the study will be the comparison of PFS per RECIST 1.1 between neratinib monotherapy versus neratinib plus fulvestrant using a stratified logrank test with an overall one-sided Type I error rate at 0.1.

All inferences will be conducted in the intent-to-treat manner with all randomized patients

evaluated according to treatment assignment that was given, and the survival function will be summarized using the Kaplan-Meier methods according to randomized treatment assignment. Final analysis will be performed after 126 PFS events are observed or at least 12 months after the last patient is enrolled on study, whichever occurs first.

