3.8.2 Definitions

Protocol Deviation: Any departure from the defined procedures set forth in the IRB-approved protocol which is *prospectively approved* prior to its implementation.

Protocol Exception: Any protocol deviation that relates to the eligibility criteria, e.g. enrollment of a participant who does not meet all inclusion/exclusion criteria.

Protocol Violation: Any protocol departure that was not *prospectively approved* by the IRB prior to its initiation or implementation.

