5.1 Ongoing Monitoring of Protocol Compliance

The Participating Institutions will be required to submit participant source documents to the DF/HCC Lead Institution or designee for monitoring. Participating Institutions may also be subject to on-site monitoring conducted by the DF/HCC Lead Institution.

The DF/HCC Lead Institution will implement on-site and virtual monitoring activities to ensure that Participating Institutions are complying with regulatory and protocol requirements, data quality, and subject safety. At minimum, the DF/HCC Lead Institution, or designee, will monitor each participating site twice a year while patients are receiving study treatment. Should a Participating Institution be monitored once and then not accrue any additional participants or participant visits, then a second monitoring visit may not be necessary.

Monitoring practices may include but are not limited to: source verification, review and analysis of the following: eligibility requirements of all participants, informed consent procedures, adverse events and all associated documentation, study drug administration / treatment, regulatory records and site trial master files, protocol deviations, pharmacy records, response assessments, and data management. Additionally, ongoing communication will occur through regularly scheduled teleconferences and by email. Source documents from Participating Institutions, will be collected at specific timepoints to support the primary and/or secondary endpoints.

On-Site Monitoring: On-site monitoring will occur on an as-needed basis. Participating

Institutions will be required to provide access to participants' complete medical record and source documents for verification during on-site visits. Upon request, Participating Institutions should provide access to regulatory documents, pharmacy records, local policies related to the conduct of research, and any other trial-related documentation maintained by the Participating site. If there are protocol compliance concerns, issues that impact subject safety or the integrity of the study, or trends identified based on areas of need, additional monitoring visits may occur.

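### The primary PFS population is all randomized patients in Sections 13.2 and 13.4 but all eligible patients in 13.7 and 13.7.2, and the cancellation rule does not say that a randomized non-starter stays in the ITT set

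*Combined protocol and SAP*

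**What the plan says.** Two sections define the efficacy population as everyone randomized. Section 13.2 gives the total of 152, "which is calculated based on the number of randomized patients and defines the intention-to-treat population for efficacy analysis". Section 13.4, on the primary analysis, says "All inferences will be conducted in the intent-to-treat manner with all randomized patients", and has the Kaplan-Meier curves drawn by randomized arm.

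Two later sections use another word. Section 13.7, under a heading about exclusions, says "All eligible participants included in the study will be evaluable for analysis". Section 13.7.2, on the primary efficacy endpoint, says "All eligible participants included in the study will be assessed for response/outcome to therapy for the primary endpoint". It goes on to keep patients with serious departures from protocol treatment, but does not mention randomized patients found to be ineligible.

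Sections 4.1 and 4.3 require the registration to be canceled when a registered participant receives no protocol therapy. Under Section 4.4, outside sites get the assigned treatment, where applicable, with the confirmation of registration, and treatment may not start before that confirmation. A canceled patient may therefore already be randomized, with her arm known. Neither section says what cancellation means for the analysis set.

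**The concern.** All randomized and all eligible are different sets whenever a randomized patient is ineligible. The protocol foresees this: Appendix E, Section 3.8.2 has a category for "enrollment of a participant who does not meet all inclusion/exclusion criteria", and the monitoring in Appendix E, Section 5.1 may include "source verification, review and analysis of the following: eligibility requirements of all participants", which can happen after the arm is known. A statistician working from 13.4 keeps such a patient; one working from 13.7.2 could leave her out and cite the text. The cancellation rule raises the same question for non-starters.

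At stake is the protection that randomization gives the primary test. Exclusions made after the arm is known can be unequal between arms and related to prognosis, and the one-sided 0.10 level then no longer holds. No blinding is described. Arm A adds injections that are charged to the patient or insurer (8.2.1), and Arm B patients may not cross over (5.6). Arm-related non-starting is therefore conceivable, but its direction cannot be told from the documents.

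**Working it through.** **1. Which population was the trial sized on?** Inputs from Section 13.2: medians 4 and 6 months (HR = 4/6), one-sided alpha 0.10, 125 events, futility look at 63 events (stop if Z < 0), 76 per arm, accrual A = 18 months, follow-up F = 6 months, 5% lost at one year.

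- Power without the look: Φ(√(125/4) × ln 1.5 − 1.2816) = Φ(2.267 − 1.282) = 0.838.
- With the look, the final critical value kept at 1.2816 and correlation √(63/125) = 0.710: P(Z₁ > 0, Z₂ > 1.2816) = 0.823, the stated 82.3%.
- Expected events per arm at month 24, with λ = ln 2/median, η = −ln(0.95)/12 and s = λ + η: 76 × (λ/s) × [1 − (e^(−sF) − e^(−s(A+F)))/(sA)]. Control 66.5, combination 58.6, total 125.1 against 125 stated.

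Both figures reproduce on all 152 randomized patients, so the sizing goes with 13.2 and 13.4. (Section 13.4 says 126 events, which gives 82.5%; that difference is separate and immaterial.)

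**2. Random loss.** Expected events at month 24 scale with the number analyzed: 125.1 × 148/152 = 121.8 with 4 lost, 118.6 with 8 and 112.0 with 16.

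- Analysis fixed at month 24: power is 0.817 with 4 lost and 0.811 with 8.
- Analysis timed as in 13.4 ("Final analysis will be performed after 126 PFS events are observed or at least 12 months after the last patient is enrolled on study", simulated as 126 events or month 30, with the futility look): power is 0.822, 0.820, 0.819 and 0.813 for 0, 4, 8 and 16 lost.

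Under the 13.4 timing, the cost is mainly delay: 125 events are expected at month 25.1, 26.6 or 31.7 with 4, 8 or 16 lost, against 24.0 with none.

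**3. Removal under no treatment effect.** The documents give no rate, arm or prognosis of loss, so every row below is an assumption. Model: 76 per arm, median 4 months in both, the accrual and dropout above, unstratified log-rank test at one-sided 0.10, analysis at 126 events or month 30, 30,000 trials per row (Monte Carlo SE about 0.002), no futility look. The subgroup from which patients are removed has the same size in both arms.

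| Patients removed | Their hazard relative to average | Type I error |
|---|---|---|
| None (full ITT, all runs) | – | 0.095–0.105 |
| 8 from Arm B only / 8 from Arm A only | 1.0 | 0.103 / 0.104 |
| 8 from each arm | 0.5 / 1.5 | 0.104 / 0.102 |
| 1 / 2 from Arm B | 0.5 | 0.110 / 0.121 |
| 4 / 8 from Arm B | 0.5 | 0.145 / 0.200 |
| 4 from B and 2 from A / 8 from B and 4 from A | 0.5 | 0.116 / 0.149 |
| 4 / 8 from Arm A | 1.5 | 0.120 / 0.142 |
| 4 / 8 from Arm A | 0.5 | 0.067 / 0.040 |
| 4 / 8 from Arm B | 1.5 | 0.083 / 0.072 |

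The planned futility look lowers each figure by about 0.003 to 0.012. A separately written simulation of 12,000 trials per scenario gave 0.143 and 0.199 for the loss of 4 and 8 good-prognosis patients from Arm B.

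**The case against.** The governing text is arguably clear already. Section 13.4 is the primary-analysis section and covers all inferences. Section 13.7 reads like template wording, and 13.7.2 says who will be assessed without saying that anyone is excluded. The affected group should also be small. Appendix E, Section 3.7.3 bars eligibility exceptions without IRB approval, 3.8.2 treats an exception as approved in advance, and eligibility is checked before registration (4.1, 4.4). Monitoring lists the eligibility of all participants, so later findings should arise in both arms, and balanced removal is harmless. All of this stands, and it makes the point minor. It does not remove the conflict: the section headed for the primary endpoint still names a different population.

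A reader might infer three stronger things, which the documents do not support.

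- *That canceled patients leave the analysis or the study.* No passage says so. Cancellation is not among the off-study criteria in 5.8, and 13.2 says "Patients will be followed for up to five years after removal from study or until death, whichever occurs first", which can be read as covering them.
- *That a never-treated patient has no disease-assessment interval and so needs a new schedule.* Section 11.1 gives an 8-week interval that is not expressly limited to treated patients. A new 8-weekly rule would add procedures and be denser than the 3 to 6 months that Section 10 sets for patients who discontinue therapy.
- *That the error rate is, or is likely to be, as high as 0.20.* That needs 8 of 76 (10.5%) lost from one arm only, all at half the average hazard. Nothing in the documents points to such a pattern.

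**Conclusion.** The concern holds as an inconsistency of wording plus an omission, of minor severity. The primary population is described in two ways with no sentence ranking them, and the cancellation rule is silent on the ITT set. Sections 13.2 and 13.4 are explicit and agree with the sizing, so the all-randomized reading should prevail.

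The consequence is conditional. Balanced or non-prognostic removal leaves the type I error at 0.102 to 0.104. Prognosis-related loss of one or two good-prognosis patients from Arm B alone gives 0.110 to 0.121, and of four to eight 0.145 to 0.200. Loss in other patterns can also push the error below 0.10. These figures rest on assumed numbers, arms and hazards, and on an unstratified test without the futility look. They show what the wording leaves open, not what is expected to happen.

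**What to change.** - In 13.7 and 13.7.2, replace the reference to eligible participants with: *All randomized participants, analyzed by assigned arm regardless of eligibility or treatment received.* Make any eligible-only or treated-only set a sensitivity analysis.
- In 4.1 and 4.3, add that canceling the registration of a randomized patient does not remove her from the ITT set or, as far as she consents, from the follow-up for progression and survival already in the protocol. No new scan schedule is needed.
- Report ineligible patients and non-starters by arm, with reasons.

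The cost is a few sentences in four sections and continued follow-up of a few untreated patients. The downside is that ineligible or never-treated patients slightly dilute the effect estimate. The change is best made before anyone sees data by arm.

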14. PUBLICATION PLAN

The results should be made public within 24 months of reaching the end of the study. The end of the study is the time point at which the last data items are to be reported, or after the outcome data are sufficiently mature for analysis, as defined in the section on Sample Size, Accrual Rate and Study Duration. If a report is planned to be published in a peer-reviewed journal, then that initial release may be an abstract that meets the requirements of the International Committee of Medical Journal Editors. A full report of the outcomes should be made public no later than three (3) years after the end of the study.

APPENDIX A PERFORMANCE STATUS CRITERIA

ECOG Performance Status Scale		Karnofsky Performance Scale	
Grade	Descriptions	Percent	Description
0	Normal activity. Fully active, able to carry on all pre-disease performance without restriction.	100	Normal, no complaints, no evidence of disease.
		90	Able to carry on normal activity; minor signs or symptoms of disease.
1	Symptoms, but ambulatory. Restricted in physically strenuous activity, but ambulatory and able to carry out work of a light or sedentary nature (e.g. , light housework, office work).	80	Normal activity with effort; some signs or symptoms of disease.
		70	Cares for self, unable to carry on normal activity or to do active work.
2	In bed <50% of the time. Ambulatory and capable of all self-care, but unable to carry out any work activities. Up and about more than 50% of waking hours.	60	Requires occasional assistance, but is able to care for most of his/her needs.
		50	Requires considerable assistance and frequent medical care.
3	In bed >50% of the time. Capable of only limited self-care, confined to bed or chair more than 50% of waking hours.	40	Disabled, requires special care and assistance.
		30	Severely disabled, hospitalization indicated. Death not imminent.
4	100% bedridden. Completely disabled. Cannot carry on any self-care. Totally confined to bed or chair.	20	Very sick, hospitalization indicated. Death not imminent.
		10	Moribund, fatal processes progressing rapidly.
5	Dead.	0	Dead.

APPENDIX B Neratinib Pill Diary

Name _____ Subject # _____ Dose _____ Cycle _____

Day	Date (DD-MM-YY)	Time Taken	No. of neratinib capsules taken
1			
2			
3			
4			
5			
6			
7			
8			
9			
10			
11			
12			
13			
14			
15			
16			
17			
18			
19			
20			
21			
22			
23			
24			
25			
26			
27			
28			

*Please take your neratinib capsules at the same time every day with food. Avoid grapefruit, grapefruit juice, grapefruit hybrids and starfruit.

*Please do not make up any missed doses (or vomited doses). If you forget to take your neratinib dose within 12 hours of the usual time, do not take it that day. Restart taking neratinib the next day.

*Neratinib can be stored at ambient temperature. If you are taking an acid-reducing medication (such as lansoprazole or ranitidine) please consult with your doctor.

Please contact your study team with any questions.

Subject Signature _____ Date _____

Reviewed by _____ Date _____

(Study staff)

APPENDIX C Patient Instructions for Management of Diarrhea

Please review these instructions with your study doctor/team. Once all of your questions are answered, sign at the bottom and make sure you are given a copy of these instructions to take home.

Diarrhea is the most common side effect you may have while participating in this study. Diarrhea usually starts within a few hours to a few days of the first dose of study drug. In order to reduce or even prevent diarrhea as far as possible, you will be supplied with anti-diarrheal medicines called loperamide and colestipol to take at the start of the study. **Use of anti-diarrheal medication is required for all enrolled subjects to help reduce or prevent diarrhea.** Loperamide and colestipol will be dispensed directly by your study doctor/team on day 1 with the instruction to initiate treatment with loperamide and colestipol on the same day as you take your first dose of neratinib.

The first dose of colestipol should be taken at least 4 hours before neratinib and loperamide. The second dose of colestipol should be taken at least 2 hours after neratinib and loperamide.

Your study doctor/team will call you on Cycle 1 Day 2, Cycle 1 Day 3, and Cycle 1 Day 4 after your first dose of study drug to find out if you are experiencing diarrhea and to provide further treatment instructions and advice if necessary.

If you are having new-onset diarrhea, persistent diarrhea or diarrhea with increase of 7 or more stools per day over usual, call your study doctor/team at phone number _____ to let them know so they can work with you to control the diarrhea. If you are dizzy or weak because of diarrhea, go to the study doctor's office or go to the hospital immediately.

Please record the number of stools and any anti-diarrheal medication taken during all cycles of the study along with the daily dose of study medication.

Information to provide when talking to your doctor

When talking to the study doctor/team I will provide as much of the information below as possible, in order to help my study doctor/team to assess my diarrhea and decide on the best treatment:

- Number of stools per day as compared to my normal bowel habits
- Presence of diarrhea during the night
- Presence of fever, dizziness, abdominal pain/cramping, or weakness
- What the stool looks like, that is, watery stools, blood, or mucus
- When I took my last study drug
- Any other information that could explain my diarrhea (food, recent travel, contact with other people with diarrhea).

1. Medications to treat diarrhea

My study doctor/team will provide me with loperamide and colestipol on day 1 with the instruction to start treatment with loperamide and colestipol along with the first dose of neratinib. I need to take the medications as directed by my study doctor/team.

R Loperamide:

- I will start loperamide with the first dose of neratinib
- I will take 2 tablet/capsule (4 mg) three times a day for the first two weeks; if I get constipated, I should contact my study doctor/team who will instruct me on how often and how much loperamide to take but I should not stop taking loperamide.
- After the first two weeks, I will take 2 tablets (4 mg) twice a day onwards through the first cycle of therapy (28 days) from the start of neratinib regardless of whether I have diarrhea or not.
- If I continue to have diarrhea while taking loperamide, I should contact my study doctor/team for additional anti-diarrheal medication and consult.
- If I have diarrhea with increase of up to 6 stools per day over usual any time after completing the first cycle of therapy and I am not taking any anti-diarrheal medication, I will take 2 tablets/capsules (4 mg) immediately after the first loose stool and then 1 tablet (2 mg) every 4 hours or after each loose stool to a maximum dose of 8 tablets/capsules (16 mg) in any 24 hour period until I haven't had any loose stool for at least 12 hours.

R Colestipol:

- I will take 2g of colestipol twice a day for the first 28 days of treatment along with the neratinib and loperamide.
 - **I will take the first dose of colestipol at least 4 hours before neratinib and loperamide prophylaxis, and I will take the second dose at least 2 hours after neratinib and loperamide prophylaxis.**
 - Take colestipol with plenty of water or other appropriate liquid. Do not cut, crush, or chew tablets.
 - Other medication (Study doctor/team to write in name of medication and instructions):
-
-

In case of more severe diarrhea and any diarrhea associated with fever, pain, infection, or dehydration, I may receive IV fluids, antibiotics and/or other medications.

2. Changes to my diet to treat diarrhea

If I have diarrhea, I will:

- Stop all lactose-containing products (milk, yogurt, cheese, etc)
- Drink 8 to 10 large glasses of clear liquids per day
- Eat frequent small meals
- Eat low fat foods such as the BRAT diet that includes **bananas, rice, applesauce, and/or toast:**

- The BRAT diet is a bland diet that is low in fat and fiber and will not irritate the stomach;
- Bananas are high in potassium and can cause constipation which can help alleviate the diarrhea
- Other similar foods are crackers, cooked cereals and pasta
- This diet is not complete in nutrients and should only be taken for a short period of time and only upon the doctor's advice.

My study doctor/team may have other suggestions for me. (Study doctor/team to write in any suggestions).

3. Study Medication adjustments

If I am experiencing loose stools or diarrhea and cannot reach my study doctor/team immediately, I will start taking anti-diarrheal medication per the instructions above until further advice is given by my study doctor/team. If I have more than 4-6 stools per day compared to normal despite taking anti-diarrheal medication for 24 hours, and I cannot reach my study doctor/team, I will stop taking the study medication and wait for further instructions from my study doctor/team.

My signature below indicates I have reviewed this information and have received the following medications:

- Neratinib Tablets
- Loperamide
- Colestipol

Study participant name

Study participant Signature and Date

Investigator delegate name

Investigator delegate Signature and Date

OR

Investigator name

Investigator Signature and Date

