5.4.3.1 Loperamide (Imodium ®)

For the first 14 days, loperamide 4 mg (2 tablets/capsules) will be self-administered orally 3 times a day (total 12 mg a day). The initial dose of loperamide will be administered orally with the first dose of neratinib. After the first 14 days, loperamide 4 mg (2 tablets/capsules) will be administered orally twice a day (total 8 mg a day) through the first cycle of therapy (Day 28) from start of neratinib dosing, whether the patient is experiencing diarrhea or not. Thereafter, loperamide will be administered as needed (not to exceed 16 mg per day) per the investigator's discretion. Commercial supply of loperamide will be used and provided by research pharmacies (cost covered by ██████████)

Loperamide Dosing

Day	Loperamide Dose
1-14	Daily dose of 12 mg in 3 divided doses of 4 mg
15-28	Daily dose of 8 mg in 2 divided doses of 4 mg
>28	Daily dose as needed (not to exceed 16 mg per day)

Loperamide Dose Adjustment

Patients are expected to take loperamide prophylaxis as directed. However, patients may require individualization of loperamide prophylaxis dose (up to a maximum dose of 16 mg per day) with the goal of titrating to 1-2 bowel movements a day.

- For patients who develop diarrhea during Cycle 1, loperamide should be increased up to a maximum of 16 mg a day.
- If a patient is unable to tolerate loperamide due to symptomatic constipation, loperamide should be held until after the first bowel movement and then resumed at a dose reduced by one level from their current level.
- For recurrent symptomatic constipation events, hold loperamide until after the first bowel movement and then resume at a dose reduced to the next lower dose level.
- If a patient is unable to tolerate once-daily loperamide due to constipation, hold loperamide and discuss subsequent loperamide dosing with the Investigator or suitably trained and qualified delegate.
- Neratinib dosing should continue if loperamide is held.

Recommended dose reductions for loperamide are listed in the table below.

Loperamide Dose Reduction Levels for Constipation.

Dose Level	Loperamide Dose	Tablets/Capsules per day
0	4 mg TID	6 tablets/capsules a day
-1	4 mg BID	4 tablets/capsules a day
-2	2 mg TID	3 tablets/capsules a day
-3	2 mg BID	2 tablets/capsules a day
-4	2 mg once a day	1 tablet/capsule a day

Abbreviations: BID = twice daily; mg=milligrams; TID= three times daily.

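### The signed patient sheet tells a constipated patient not to stop loperamide, although every constipation rule in 5.4.3.1 begins with a hold; separately, one octreotide step in 5.4.3.3 is void under its own heading

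*Combined protocol and SAP*

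**What the plan says.** Appendix C is a take-home document. The patient is asked to "sign at the bottom and make sure you are given a copy of these instructions to take home". In its part 1, on medications, the bullet for the first two weeks of loperamide says that a patient who gets constipated should "contact my study doctor/team who will instruct me on how often and how much loperamide to take but I should not stop taking loperamide". The same part also states "I need to take the medications as directed by my study doctor/team". The next bullet, "After the first two weeks, I will take 2 tablets (4 mg) twice a day onwards through the first cycle of therapy", does not mention constipation. Part 3 contains the sheet's only stop instruction. It concerns the study medication, for a patient whose diarrhea persists despite a day of treatment and who cannot reach the team.

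Section 5.4.3.1 handles constipation with three rules:

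- "If a patient is unable to tolerate loperamide due to symptomatic constipation", then "loperamide should be held until after the first bowel movement and then resumed at a dose reduced by one level".
- "For recurrent symptomatic constipation events, hold loperamide until after the first bowel movement", followed by restarting at the next lower level.
- "If a patient is unable to tolerate once-daily loperamide due to constipation, hold loperamide and discuss subsequent loperamide dosing" with the investigator or a delegate.

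It adds that neratinib carries on during a loperamide hold, and it gives a five-level reduction table.

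Section 5.4.3.3 sets out treatment of diarrhea in blocks. The block for Days 1-28 has a Grade 2 octreotide step limited to the first 28 days. The block for new-onset Grade 1 or 2 diarrhea after day 28 repeats that step almost word for word, with the same limit.

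**The concern.** A patient who is told by phone to hold loperamide would have at home a signed sheet saying not to stop it. Nothing on the sheet says that the team may order a hold, or that neratinib continues if it does. Because the constipation clause sits inside the first-two-weeks bullet, its reach over the rest of the cycle is also unclear. At stake is whether a patient with troublesome constipation follows the protocol's rule or the sheet.

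The octreotide step raises a different problem. A clinician treating new Grade 2 diarrhea after day 28 finds a step under the right heading whose own condition excludes that patient.

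**Working it through.** No plan figure is involved, so the check sets the texts side by side.

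**Loperamide.** Inputs: the three rules and the reduction table in 5.4.3.1, and the whole of Appendix C.

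| Case in 5.4.3.1 | First action in the protocol | What the sheet tells the patient |
|---|---|---|
| Symptomatic constipation, loperamide not tolerated | Hold, then restart one level lower | Call the team; do not stop |
| Recurrent symptomatic constipation | Hold, then restart at the next lower level | Same |
| Once-daily loperamide not tolerated | Hold and discuss; no set restart | Same |

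Rules that begin with a hold: 3 of 3. Mentions of a loperamide hold in Appendix C: 0.

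Next, could a change in how often and how much is taken replace a hold? Daily dose by level (tablets or capsules of 2 mg):

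- Level 0: 3 × 4 mg = 12 mg
- Level -1: 2 × 4 mg = 8 mg
- Level -2: 3 × 2 mg = 6 mg
- Level -3: 2 × 2 mg = 4 mg
- Level -4: 1 × 2 mg = 2 mg

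For mild constipation a lower dose set by the team fits both texts. In the first two rules a pause ordered by the team can be squared with the sheet only by reading its last clause as a ban on stopping unprompted. At level -4 the table offers nothing lower, so the third rule's only action is a hold without a set restart. That case is remote: from level 0 it takes four one-level reductions and then a further intolerance.

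**Octreotide.** Inputs: the heading and the drug steps of the after-day-28 block in 5.4.3.3.

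- Days covered by the heading: day > 28.
- Days allowed by the Grade 2 octreotide step: day ≤ 28.
- Overlap: none.

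The block has three drug steps (loperamide; Lomotil for persistent Grade 1; octreotide for Grade 2), so 1 of 3 cannot apply on any day under its heading. The matching step in the Days 1-28 block is consistent with its heading, and the Grade 3-4 octreotide step has no day limit. The likeliest explanation is that the limit was carried over from the Days 1-28 text.

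**The case against.** The strongest reply is that the sheet, read as a whole, does not forbid a hold. It sends the patient to the team, lets the team set frequency and amount, and says medicines are taken as the team directs. A pause until the first bowel movement can be called a change in frequency, and not stopping reads naturally as not ending the drug on one's own initiative. Section 5.4.3.2 gives providers discretion to change loperamide or colestipol when a patient tolerates them badly. The investigator must review the sheet with the patient, and staff phone on days 2, 3 and 4 of Cycle 1 (5.4.3). All of this stands, and it makes the conflict narrow. It does not put the intended meaning on the page, and it does not supply the missing hold.

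Three stronger readings are tempting and are not supported:

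- A reader might infer that the sheet bars the team from ordering a hold, or that every constipated patient gets contradictory instructions. The sheet covers any constipation, whereas the hold rules cover constipation that is symptomatic and not tolerated, or recurrent, or that persists on once-daily dosing. Team direction remains in force throughout.
- A reader might infer that the later part of Cycle 1 has no constipation instruction at all. That depends on whether the clause is tied to its bullet or read as general. If it is tied to the bullet, the clause cannot contradict the hold rules in the later weeks; if it is general, there is no gap. The text only supports saying that its reach is unclear.
- A reader might infer that octreotide is unavailable for Grade 2 diarrhea after day 28. Section 5.4.3 recommends second-line agents, octreotide included, when appropriate and without a day limit, and the Grade 2 step is itself only something to consider.

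**Conclusion.** The point holds in a limited form: two operative safety instructions are wrong as written. The loperamide clause has no exception for the holds that open all three constipation rules, and at level -4 no dose reduction can take the place of a hold. The octreotide step cannot apply under its own heading.

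The effect is small. The documents give no rate of constipation on this prophylaxis, so no number of affected patients can be stated. The safeguards make it likely that a patient who calls will be managed correctly. The judgment about the sheet rests on reading its clause as it stands; the author probably meant that the patient should not stop unprompted. Sample size, visits and the PFS analysis are unaffected. Because the sheet is signed and taken home, the loperamide clause is better treated as a patient-safety wording correction than as an editorial matter.

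**What to change.** **Appendix C, part 1.** Replace the clause with: *I should not stop loperamide on my own; my study doctor/team may tell me to hold it, and will tell me whether, when and at what dose to restart. I should not stop neratinib because of a loperamide hold; the diarrhea instructions in part 3 still apply.* Place it in its own bullet covering the first cycle. Saying that the team decides whether to restart makes the wording fit level -4, where no lower dose exists. Keeping part 3 in force avoids overriding the instruction to stop study medication when diarrhea persists and the team cannot be reached.

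**Section 5.4.3.3, block for diarrhea after day 28.** Delete from the Grade 2 octreotide step the phrase that limits it to the first 28 days of treatment. Leave the Days 1-28 block unchanged.

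**Cost.** A minor amendment, with IRB approval and submission to local IRBs by participating institutions (Appendix E, 2.3 and 3.2), and a re-issued patient sheet. There is no change to sample size, visit schedule or analysis.
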